4.6.5.10. Malignancy

Malignancy will be considered as an AESI. The counts and percentages of participants with treatment-emergent malignancy will be summarized by treatment and PT ordered by decreasing frequency. Detailed searching criteria can be found in Appendix 7 (Section 6.7).

4.6.5.11. Renal Safety

Laboratory measures related to renal safety will be analyzed as specified for laboratory measurements in Section 4.6.3.6.

Additionally, 2 shift tables examining renal function will be created. A minimum-to-minimum shift table of estimated glomerular filtration rate (eGFR) will be estimated by the Chronic Kidney Disease Epidemiology Collaboration (CKD-EPI) equation with units of mL/min/1.73m², using categories of <30, ≥30 to <45, ≥45 to <60, ≥60, and ≥90 mL/min/1.73m². A max-to-max shift table of urine albumin-to-creatinine ratio (UACR) will be created, using the categories of UACR<30 mg/g, 30 mg/g ≤UACR≤300 mg/g, and UACR>300 mg/g (respectively, these represent normal, microalbuminuria, and macroalbuminuria).

Mixed model for repeated measure analyses for eGFR and UACR will be provided. Log transformation will be performed for UACR.

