Allowable Deviation (days)		±3	±3	±3	±3	±3	±3	±3	±3	±3	±3	±3	±3	±3	±3	±3	±3	±3	±3	±3	±3	±3	±3	±3	±3	±3	±3	±7	±7		±3
Fasting Visit	X	X		X		X		X		X	X	X	X	X	X	X			X			X			X			X	X	X	X
Telephone Visit			X		X		X		X								X	X		X	X		X	X		X	X				
Lifestyle Program Instruction only			X		X		X		X																						
Chemistry panel (includes Cr for eGFR calculation and glucose)	X									X			X			X				X			X			X			X	X	X
	The CKD-EPI equation will be used by the central lab to estimate and report eGFR.																														
Insulin	X									X			X			X			X			X			X			X		X	X
C-peptide	X									X			X			X			X			X			X			X		X	X
Lipid panel	X									X						X													X	X	X
Free fatty acids	X									X						X												X	X	X	
Serum pregnancy	X									X																					
	For women of childbearing potential only.																														
Urine pregnancy (local)										X			X			X			X			X			X			X		X	
	A urine pregnancy test must be performed at Visit 10 with the result available prior to first injection of study drug(s) for women of childbearing potential only. Additional pregnancy tests (beyond those required by the SoA) should be performed at any time during the trial if a menstrual period is missed, there is clinical suspicion of pregnancy, or as required by local law or regulation.																														
Follicle-stimulating hormone test	X																														
	Follicle-stimulating hormone test is to be performed at Visit 1 for postmenopausal women at least 40 years of age with an intact uterus, not on hormone therapy, and who have had spontaneous amenorrhea for more than 1 year without an alternative medical cause.																														
Calcitonin	X									X			X			X												X		X	X
Pancreatic amylase	X									X			X			X												X		X	X
Lipase	X									X			X			X												X		X	X
Urinary albumin/creatinine ratio	X									X						X												X		X	X
Cystatin-c	X									X						X												X		X	X

Visit	1	2	3	4	5	6	7	8	9	10	11	12	13	14	15	16	17	18	19	20	21	22	23	24	25	26	27	28	99	ED	801		
Week of Treatment	-14	-12	-11	-10	-9	-8	-6	-4	-2	0	4	8	12	16	20	24	28	32	36	40	44	48	52	56	60	64	68	72	72		4 wks Post TxP		
Allowable Deviation (days)		±3	±3	±3	±3	±3	±3	±3	±3	±3	±3	±3	±3	±3	±3	±3	±3	±3	±3	±3	±3	±3	±3	±3	±3	±3	±3	±7	±7		±3		
Fasting Visit	X	X		X		X		X		X	X	X	X	X	X	X			X			X			X			X	X	X	X		
Telephone Visit			X		X		X		X								X	X		X	X		X	X		X	X						

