4.6.3.6. Clinical Laboratory Evaluation

Descriptive summaries at each planned visit, by treatment group, will be provided for the baseline and postbaseline values, and change from baseline values. The associated descriptive summaries will be presented in SI units and CN units. Limits from the performing laboratory will be used to define low and high.

Observed and change from baseline values for each visit may be displayed in plots for participants who have both a baseline and at least 1 postbaseline planned measurement. Baseline is defined in [Table GPHM.4.1](#). Unplanned measurements will be excluded from plots.

A shift table will be provided including unplanned measurements. The shift table will include the number and percentage of participants within each baseline category (minimum value is low, normal, high, or missing) versus each postbaseline category (minimum value is low, normal, high, or missing) by treatment. The Fisher's exact test will be used to compare percentages of participants who shift from normal/high to low between treatments.

For qualitative laboratory analytes, the number and percentage of participants with normal and abnormal values will be summarized by treatment.

A listing of abnormal findings will be created for laboratory analyte measurements, including qualitative measures. The listing will include participant identification, treatment group, laboratory collection date, study day, analyte name, and analyte finding.

The MMRM model, or ANCOVA (if the MMRM model is not applicable), will be used for the analysis during the treatment period for the continuous measurements for selected lab tests.

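### The eGFR shift table has overlapping top bands (≥60 and ≥90), and the SAP names no analysis of the collected cystatin-C to check creatinine-based eGFR

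*SAP*

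**What the plan says.** SAP 4.6.5.11 (Renal Safety) plans a minimum-to-minimum eGFR shift table "using categories of <30, ≥30 to <45, ≥45 to <60, ≥60, and ≥90" mL/min/1.73 m². In the SAP, eGFR "will be estimated by the Chronic Kidney Disease Epidemiology Collaboration (CKD-EPI) equation", and the filtration marker is not named. The Protocol's Schedule of Activities (1.3) supplies it: the row is headed "Chemistry panel (includes Cr for eGFR calculation and glucose", and its note reads "The CKD-EPI equation will be used by the central lab to estimate and report eGFR".

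The same SAP section adds continuous models ("Mixed model for repeated measure analyses for eGFR and UACR will be provided") and a second shift table ("A max-to-max shift table of urine albumin-to-creatinine ratio (UACR) will be created"). It also sends renal laboratory measures to the general laboratory section: "Laboratory measures related to renal safety will be analyzed as specified for laboratory measurements in Section 4.6.3.6". SAP 4.6.5.11.1 and 4.6.5.11.2 add acute renal, chronic kidney disease and dehydration events, with severe or serious cases treated as events of special interest.

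Cystatin-C has its own row in the Schedule of Activities at Visits 1, 10, 16 (Week 24), 28 (Week 72), early discontinuation and 801, and it is in the laboratory list in Protocol 10.2. The SAP does not mention it.

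**The concern.** There are two separate points.

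**Bands.** A shift table needs categories that exclude one another. Here the fourth category contains the fifth, so a programmer must either guess the intended cut or count the same participant twice. The affected movement is from 90 or above into the range 60 to below 90.

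**Marker.** The eGFR shift table and the eGFR MMRM use the same creatinine-based value, so one cannot check the other. Protocol 9.2 assumes a between-arm difference of at least 12% in percent weight change. If weight loss on that scale lowers creatinine generation, calculated eGFR rises without any change in filtration, and more so on tirzepatide than on placebo. That is the reassuring direction, in a trial whose protocol (8.3.2.12) warns that gastrointestinal events may lead to dehydration and worse renal function. A second filtration marker is already being measured, but no analysis is assigned to it by name.

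**Working it through.** The plan states no figure to reproduce here, so there are two direct checks.

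**1. Bands.** Inputs: the five categories in SAP 4.6.5.11. Each eGFR from 0 to 150 in steps of 0.1 was assigned to every category it satisfies.

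| eGFR values | Rows as printed | Rows with the fourth band ≥60 to <90 |
|---|---|---|
| 0 to 89.9 (900 values) | one | one |
| 90 to 150 (601 values) | two (≥60 and ≥90) | one |

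Example moves:

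| Move | As printed | With the fourth band closed |
|---|---|---|
| 95 to 65 | ≥60 or ≥90 at baseline, then ≥60: no shift or one row | ≥90 to 60–<90: one row |
| 95 to 58 | ends in 45–<60 | ends in 45–<60 |

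The ambiguity is confined to values of 90 or more. Any fall below 60 lands in one row under either version.

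**2. Possible masking.** Inputs:
- Marker: creatinine (Protocol 1.3).
- Assumption, not in the documents: creatinine generation falls by a fraction g, taken from 0% to 10%.
- Simplification: serum creatinine = generation / GFR, and eGFR is proportional to 1 / creatinine.

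With a true fractional fall t in GFR:

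apparent eGFR ratio = (1 − t) / (1 − g)

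For t = 10% and a baseline of 65, true GFR after the fall is 65 × 0.90 = 58.5.

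| g | Ratio | Apparent change | eGFR shown |
|---|---|---|---|
| 0% | 0.90 / 1.00 = 0.900 | −10.0% | 58.5 |
| 5% | 0.90 / 0.95 = 0.947 | −5.3% | 61.6 |
| 10% | 0.90 / 0.90 = 1.000 | 0.0% | 65.0 |

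At g = 0% there is no bias. At 5% or more, this participant's crossing below 60 does not appear in the shift table, and the MMRM carries the same error. The last row does not depend on the 1/creatinine simplification: when generation and GFR fall in equal proportion, serum creatinine does not move, so no creatinine equation will register a change.

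**3. Does the general laboratory section fill the gap?** SAP 4.6.3.6 gives by-visit summaries ("Descriptive summaries at each planned visit, by treatment group, will be provided for the baseline and postbaseline values, and change from baseline values"), which would include cystatin-C if it counts as a renal measure. Its shift table uses minimum values, and its Fisher's test compares shifts to low. A filtration marker rises as filtration falls, so that test looks the wrong way. MMRM or ANCOVA is reserved for selected tests that are not listed.

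**The case against.** The strongest reply has four parts.

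- **The overlap is a dropped upper limit.** The list is ordered and has its own ≥90 row, so ≥60 to <90 is the evident intent. The UACR bands in the same section and the BMI bands in SAP 4.7.2.1 are exclusive. This stands: it is a drafting slip. A prespecified table should still not need interpretation.
- **Other renal analyses exist.** A reader might infer that renal safety rests on this table and on creatinine eGFR alone, so that a loss of kidney function could go unseen. The documents do not support that. They also plan UACR analyses, acute renal and dehydration events and, in Protocol 9.4.4.4.4, a between-arm comparison of treatment-emergent high or low laboratory values, which on its terms would cover a high cystatin-C. The eGFR MMRM also registers movement within the upper range, whatever the bands. What remains is narrower: UACR measures albuminuria rather than filtration, event analyses depend on events being recognised and reported, and SAP 4.6.3.6 sets out no test for rising values.
- **The creatinine effect is not in the documents.** This stands. Neither document says that weight loss lowers creatinine generation, that cystatin-C is free of such an effect, or how much lean tissue is lost; the 12% concerns total weight. Nor do they say that most participants start at 90 or above, since exclusion criterion 11 removes only eGFR below 30. It would be wrong to state that treatment does bias eGFR here.
- **Cystatin-C is sampled too sparsely for acute events.** This also stands. Escalation lasts 20 weeks, and the first scheduled post-randomization draw is at Week 24.

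**Conclusion.** The band overlap is certain and minor. It affects only values of 90 or more, can record a move from ≥90 to 60–<90 as no shift, and cannot hide a fall below 60.

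The marker point is conditional. It is certain that both eGFR analyses share creatinine and that the SAP names no analysis of the cystatin-C it will have. Whether this matters depends on the assumed fall in creatinine generation: none at 0%, and complete masking of a true 10% GFR decline at 10%. The comparison also assumes that cystatin-C is less affected by weight loss than creatinine, which the documents do not address. It supports a sensitivity analysis, not a finding that the renal assessment is unsound. No efficacy result, sample size, power or alpha is affected.

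**What to change.** 1. In SAP 4.6.5.11, write the bands as <30, ≥30 to <45, ≥45 to <60, ≥60 to <90, and ≥90 mL/min/1.73 m².
2. State in the same section that the main eGFR is creatinine-based. Add, as a supportive sensitivity analysis, a change-from-baseline analysis and a minimum-to-minimum shift table of cystatin-C-based eGFR, naming the equation to be used.
3. Show these beside the creatinine versions, restricted to visits where both markers are drawn. The restriction matters for the shift table: chemistry is drawn more often (Week 12, for example), and a minimum over more visits tends to be lower whichever marker is used.

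The cost is a wording change and a small set of extra displays from data already collected, with no new samples or visits. The limitation should be stated in the SAP: with on-treatment cystatin-C scheduled only at Weeks 24 and 72, the analysis informs sustained change in filtration. Acute events during escalation remain covered by the acute renal and dehydration event analyses. If the two estimates differ, the report will need a short interpretation.

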4.6.5.11.1. Acute Renal Events

Acute renal events, including those associated with chronic renal failure exacerbation, will also be captured.

Severe/serious renal events from the SMQ search below will be considered AESI.

The counts and percentages of participants with acute renal events will be summarized by treatment by using MedDRA PTs contained in any of the following SMQs:

- **Acute renal failure:**
 - narrow terms in the Acute renal failure SMQ (20000003)
- **Chronic kidney disease:**
 - narrow terms in the Chronic kidney disease SMQ (20000213).

In addition, a listing of participants with treatment-emergent acute renal events may be provided, if deemed necessary.

4.6.5.11.2. Dehydration

Dehydration events will be captured in the following SMQ and summarized. Severe/serious dehydration events will be considered AESI:

- narrow terms in the Dehydration SMQ (20000232).

The counts and percentages of participants with dehydration will be summarized by treatment and PT and ordered by decreasing frequency. A listing of participants with treatment-emergent dehydration events may be provided, if deemed necessary.

4.6.5.12. Thyroid Safety Monitoring

4.6.5.12.1. Calcitonin

The number and proportion of participants with a maximum postbaseline calcitonin value in the following thresholds will be provided by treatment and baseline calcitonin value (≤ 20 ng/L, >20 ng/L to ≤ 35 ng/L, >35 ng/L) and postbaseline value (≤ 20 ng/L, >20 ng/L to ≤ 35 ng/L, >35 ng/L to ≤ 50 ng/L, >50 ng/L to ≤ 100 ng/L, and >100 ng/L).

4.6.5.12.2. C-Cell Hyperplasia and Thyroid Malignancies

Thyroid malignancies and C-cell hyperplasia will be considered AESI. Detailed searching criteria can be found in Appendix 6.7 (Section 6.7).

The counts and percentages of participants with treatment-emergent thyroid C-cell hyperplasia and malignancies will be summarized by treatment and PT ordered with decreasing frequency. In addition, a listing of participants with treatment-emergent thyroid C-cell hyperplasia and neoplasms may be provided if deemed necessary.

4.6.5.15. Abuse Potential

To identify AE terms suggestive of abuse liability potential, narrow terms from the Drug abuse and dependence SMQ (20000101) will be used. Counts and percentages of participants will be summarized by treatment group with decreasing frequency.

4.7. Other Analyses

4.7.1. Health Outcomes

The patient-reported outcome questionnaires will be analyzed using the mITT population on the EAS, unless specified otherwise.

Item-level missingness is dealt with as per the instrument developers' instruction.

Additional psychometric analyses may be performed by the Value Evidence Outcomes group at Lilly and documented in a separate analysis plan.

4.7.1.1. Patient Global Impression of Status for Physical Activity

The counts and percentages of participants for Patient Global Impression of Status for Physical Activity (PGIS) response categories will be summarized by nominal visit and by treatment. A shift table from baseline to postbaseline of 5 PGIS response categories at each postbaseline visit by treatment will be created.

4.7.1.2. Short-Form-36 Health Survey Version 2, Acute Form

Per copyright owner, the QualityMetric Health Outcomes™ Scoring Software 4.5 will be used to derive the following domain and component scores:

- Mental Component Summary (MCS)
- Physical Component Summary (PCS)
- Physical Functioning (PF) domain
- Role-Physical domain (RP)
- Bodily Pain (BP) domain
- General Health domain (GH)
- Vitality domain (VT)
- Social Functioning domain (SF)
- Role-Emotional domain (RE), and
- Mental Health domain (MH).

For each above domain and component summary score parameter, the raw scores will be transformed into the domain scores (t-scores), and the following analyses for the actual value and change from baseline value will be conducted:

- descriptive summaries by treatment group, and

- analysis described in [Table GPHM.4.3](#) and [Table GPHM.4.4](#).

The empirical cumulative distribution function (eCDF) curves of the change from baseline to 72 weeks in Short Form-36 Version 2 Health Survey acute form (SF-36v2) PF domain scores will be provided by treatment group.

If data allow, analysis for SF-36v2 PF domain scores described in [Table GPHM.4.3](#) will be conducted to evaluate the treatment effect in participants who have limitations in PF at baseline, which are defined as PGIS responses at baseline of “moderately limited,” “very much limited,” or “extremely limited.”

4.7.1.3. Impact of Weight on Quality of Life-Lite Clinical Trials

The following parameters will be included from the Impact of Weight on Quality of Life-Lite-Clinical Trials Version (IWQOL-Lite-CT):

- IWQOL Lite CT total score (all items: items 1 through 20)
- PF composite score (5 items: items 1 through 3, 16, 17)
- Physical composite score (7 items: item 1 through 5, 16, 17), and
- Psychosocial composite score (13 items: item 6 through 15, 18, 19, 20).

The IWQOL-Lite-CT total and composite scores range from 0 to 100, with higher scores reflecting better levels of functioning.

The IWQOL-Lite-CT scores are computed according to the IWQOL-Lite scoring rules (Kolotkin et al. 2002) as follows:

For total and each composite score, the following analyses for the actual value and change from baseline value will be conducted:

- descriptive summaries by treatment group, and
- ANCOVA analysis described in [Table GPHM.4.3](#) and [Table GPHM.4.4](#).

If data allow, IWQOL-Lite-CT PF composite score analysis described in [Table GPHM.4.3](#) will be conducted to evaluate the treatment effect in participants who have limitations in PF at baseline (as defined in Section [4.7.1.2](#)).

4.7.1.4. EQ-5D-5L

For the utility score and the Visual Analog Scale (VAS) scores, the following analyses of the actual value and change from baseline value will be conducted:

- descriptive summaries by treatment group, and
- analyses described in [Table GPHM.4.4](#).

4.7.2. Subgroup Analyses

Efficacy subgroup analyses will be guided by the treatment-regimen estimand in the FAS and the efficacy estimand in the EAS.

Subgroup analyses may be done by country to support local regulatory registrations.

4.7.2.1. Subgroup Analysis of Body Weight Change

Subgroup analyses by the following baseline characteristics will be provided:

- age (<65, ≥65 years)
- sex (female and male)
- race
- ethnicity
- BMI at randomization (<30, ≥30 and <35, ≥35 and <40, ≥40 kg/m²)
- region of enrollment (US, outside of US), and
- percentage of body weight reduction at the end of lead-in (<10% and ≥10%).

The outcome measures for the subgroup analyses will include

- percent change in body weight from randomization at 72 weeks, and
- proportion of participants achieving at least 5% body weight reduction from randomization to 72 weeks.

For the percent change in body weight from randomization at 72 weeks, for each subgroup analyses aforementioned, the following analyses will be conducted.

Treatment Regimen Estimand

- Conduct the ANCOVA model on the subgroup only with terms of treatment group, country/pooled country, and sex as fixed effects and baseline body weight as a covariate. Missing body weight measurements at 72 weeks will be imputed using the imputation method described in Section 4.3.2.3.
- Full ANCOVA model - Treatment group, subgroup, treatment-by-subgroup-interaction, country/pooled country, and sex as fixed effects and baseline body weight as a covariate. Missing body weight measurements at 72 weeks will be imputed using the imputation method described in Section 4.3.2.3.

Efficacy Estimand

- Conduct the MMRM model on the subgroup only with terms of treatment group, visit, treatment-by-visit-interaction, country/pooled country, and sex as fixed effects, and baseline body weight as a covariate. The variance-covariance structure for within-patient errors will be same as Section 4.3.2.2.
- Full MMRM model - Treatment group, visit, subgroup, treatment-by-visit-interaction, treatment-by-subgroup-interaction, subgroup-by-visit-interaction, treatment-visit-subgroup-interaction, country/pooled country, and sex as fixed effects and baseline body weight as a covariate. The variance-covariance structure for within-patient errors will be same as Section 4.3.2.2.

For the percentage of participants achieving at least 5% body weight reduction at 72 weeks, for each subgroup analyses aforementioned, the following analyses will be conducted.

Treatment Regimen Estimand

- Conduct the logistic regression model on the subgroup only with terms of treatment group, country/pooled country, and sex as fixed effects and baseline body weight as a covariate. Missing body weight measurements at 72 weeks will be imputed using the imputation method described in Section 4.3.2.3, then the continuous measurements will be dichotomized into status of achieving at least 5% body weight reduction (Yes or No).
- Full logistic regression model - Treatment group, subgroup, treatment-by-subgroup-interaction, country/pooled country, and sex as fixed effects and baseline body weight as a covariate. Missing body weight measurement at 72 weeks will be imputed using the imputation method described in Section 4.3.2.3, then the continuous measurements will be dichotomized into status of achieving at least 5% body weight reduction (Yes or No).

Efficacy Estimand

- Conduct the logistic regression model on the subgroup with terms of treatment group, country/pooled country, and sex as fixed effects and baseline body weight as covariate. Missing body weight measurement at 72 weeks will be imputed by the predicted value from the MMRM model on the subgroup aforementioned, then the continuous measurements will be dichotomized into status of achieving at least 5% body weight reduction (Yes or No).

- Conduct the logistic regression model with terms of treatment group, subgroup, treatment-by-subgroup-interaction, country/pooled country, and sex as fixed effects and baseline body weight as a covariate. Missing body weight measurement at 72 weeks will be imputed by the predicted value from the full MMRM model aforementioned, then the continuous measurements will be dichotomized into status of achieving at least 5% body weight reduction (Yes or No).

